3.2 Treatment Variables

Concomitant Medication Review. Subjects will be asked about their use of medications (over the counter and prescription) and substances that may alter subjects' response to the study medication. The Study Physician/Health Care Provider will advise as to whether other medications being taken are contraindicated and prescribe appropriate action from there (i.e., discontinuation of the study medication). The concomitant medication review will be completed at every study visit following the Intake.

Pill Count/Adherence. Medication adherence will be assessed by pill count at each study visit or telephone session [42]. We will assess patch use by participants' self-report and collect unused patches at the end of the week.

Side Effects. A checklist of side effects based on the product insert will be administered to participants at all study visits after the Intake. The frequency and severity of common side effects of RAM [43] and TN [30, 44] will be rated on a 0 (none) to 3 (severe) scale. An open-ended side effects question will also be included. Furthermore,

participants will receive written instructions to call the Health Care Provider/Study Physician should they experience any severe side effects or adverse events between study visits.

3.3 Intermediate Outcomes

Subjective Sleep Measures: As in [name] prior work, subjects will complete sleep diaries daily within 1h of getting out of bed and prior to going to sleep and will provide time-stamped phone records for time to bed and time awake [45-48]. These well-validated sleep diaries assess subjective SOL, total sleep time, number of awakenings and perceived quality of sleep. The diaries will be used to verify the sleep parameters derived from the SensewearPro® armbands [49, 50].

The Pittsburgh Sleep Quality Index (PSQI) is a 9-item measure that assesses the quality and patterns of sleep over the past month. It measures seven areas: subjective sleep quality, sleep latency, sleep duration, habitual sleep efficiency, sleep disturbances, use of sleep medication, and daytime dysfunction. Scoring is based on a 0 to 3 scale, whereby 3 reflects the negative extreme. A sum of "5" or greater indicates a "poor" sleeper [51]. The PSQI has good internal consistency ($\alpha=0.83$), validity, and reliability, and is sensitive to treatment [52, 53]. The outcome is the global PSQI score and will be evaluated as a moderator of RAM's effects on abstinence.

Sleep Efficiency (SensewearPro armbands): A multi-method approach is necessary to capture different components of insomnia symptoms [54], such as self-report, polysomnography (PSG) or actigraphy [50]. Compared to PSG, actigraphy provides concordance rates between 80% and 95% for wake/sleep detection, enables data collection for weeks to months, and is less expensive [50, 55, 56]). The SensewearPro® armbands (BodyMedia, Inc. Pittsburgh, PA) measure body movement, like actigraphy, and acquire additional physiological signals, including surface body temperature, galvanic skin response, and heat flux [57]. The armbands provide 89% concordance with PSG data and identify sleep and wakefulness with moderate to high sensitivity and specificity [57]. Subjects will wear the armband during each phase (weeks 1, 2, 5, and 6), and will be provided \$4/day for each day they wear the armband and complete the sleep diary plus \$50 if they provide at least 18 of 22 days of data (85%). Subjects will be instructed to remove the armband only for bathing purposes or water activity. The data will be downloaded to the Sensewear Professional software (v8.0; Bodymedia, Pittsburgh, PA) at each visit to confirm compliance using a threshold of 90% on body time. Following PSG standards, the first and last nights will not be analyzed to allow for adaptation [50, 55, 56]. The outcome is sleep efficiency. Participants will not be responsible for lost or otherwise compromised armbands.

Depression symptoms. The 20-item Center for Epidemiological Studies on Depression scale (CESD) will assess depressive symptoms [58, 59]. It has high internal consistency ($\alpha=0.85$) and scores greater than 16 correlate with clinical ratings of depression [60]. Participants will rate the intensity of their symptoms in the past week on the following scale: 0 = rarely, or none of the time (less than once a day), 1 = some, or a little of the time (1-2 days), 2 = occasionally, or a moderate amount of time (3-4 days), 3 = most, or all of the time (5-7 days) and a summary score will be calculated. The CESD will be administered at the Intake and on the last visit of each Baseline and Quit Assessment week.

Withdrawal Symptoms. The "Minnesota Nicotine Withdrawal Scale - Revised version"(MNWS_R) [61] captures the current state of nicotine withdrawal [62, 63]. The scale assesses eight DSM-IV items of nicotine withdrawal including: dysphoria or depressed mood, insomnia, irritability/frustration/anger, anxiety, decreased heart rate, difficulty concentrating, restlessness, and increased appetite/weight gain. Participants will rate the intensity of their symptoms on the following scale: 0 = none, 1 = slight, 2 = mild, 3 = moderate, 4 = severe and a summary score will be calculated. This will be administered at all study visits (except the Intake). Withdrawal will be assessed using a 24-h time reference for all visits following the Intake.

Craving. The 10-item brief QSU questionnaire on smoking urges [64] will be used to assess craving for cigarettes during the medication run-up period. The QSU-B contains 2 subscales (anticipation of reward, relief from negative affect). Craving has also been related to long-term cessation outcome in many, but not all, clinical studies [65]. This will be administered at all study visits (except the Intake). Similar to withdrawal symptoms, craving will be assessed using a 24-h time reference at all visits following the Intake.

Mood: Positive and Negative Affect. The Positive and Negative Affect Schedule (PANAS) [66], a 20-item Likert-format self-report measure, will be used to assess Positive Affect (PA; 10 items, e.g., enthusiastic, strong) and Negative Affect (NA; 10 items, e.g., distressed, upset), two dominant and generally orthogonal dimensions of affect. PA and NA (PANAS) will be assessed at all study visits (except the Intake). PA and NA will be assessed using a 24-h time reference for all visits following the Intake.

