Names of Investigators:

Name	Department (all at UPenn)
[name]., Principal Investigator [name] [contact] [contact]	Psychiatry
[name]., Co-I	Psychiatry
[name]., Co-I	Psychiatry
[name], Ph.D., Study Physician	Psychiatry

PROTOCOL TITLE

1. Full Title

Repurposing melatonin receptor agonists as adjunct treatments for smoking cessation. (NCT02560324)

2. Brief Title

Effect of ramelteon on smoking abstinence

STUDY SPONSORSHIP

1. Funding Sponsor

National Institute on Drug Abuse (R21 DA040902)

2. Primary Sponsor

[name]., Director, CIRNA

PROTOCOL ABSTRACT

There is a need for novel approaches to optimize smoking cessation treatment to help more smokers quit. Sleep disturbance during nicotine withdrawal may be an important treatment target since existing treatments do not mitigate withdrawal-related sleep disturbance and difficulty sleeping predicts smoking relapse. We hypothesize that the FDA-approved melatonin receptor agonist, ramelteon, combined with transdermal nicotine replacement therapy (TN), will promote abstinence by attenuating withdrawal-related sleep disturbance. Using a well-validated medication screening paradigm, we propose a within-subject, placebo-controlled crossover design with one within-subjects factor of medication (ramelteon vs. placebo). Treatment-seeking smokers (n=50) will complete this 6-week study (two 2-week phases separated by a 2-week washout). Each phase includes 1 week of *ad libitum* smoking (baseline) and 1 week of medication (8mg ramelteon or placebo) plus TN while trying to abstain (quit assessment). Small monetary incentives will be provided for biochemically-confirmed abstinence. Subjects will keep daily sleep diaries and wear an armband while sleeping which provides objective indices of sleep (SensewearPro®). The primary outcome will be the number of biochemically-confirmed days abstinent (out of five). Intermediate outcomes include sleep onset latency (self-report) and sleep efficiency (SensewearPro® armband). These data will lay the foundation for a larger Phase IIb clinical trial.

OBJECTIVES

1. Overall Objectives

The objective of this proof-of-concept pilot study is to evaluate ramelteon as a potential smoking cessation aid in treatment-seeking smokers.

2. Primary Outcome Variable(s)

The primary outcome is the total number of days abstinent (biochemically verified) during a 5-day quit attempt.

3. Secondary Outcome Variable(s)

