3.4 Smoking Outcomes

Smoking Rate (TLFB). We will assess the number of cigarettes smoked on each day throughout the study. A standard timeline follow-back (TLFB) method will be used [67], as we have done previously [68] to assess self-reported smoking rate. During each quit week, abstinence will be assessed daily by self-report of no smoking at all over the prior 24 hours and an expired-air CO less than 5 ppm (except for the Monday visit when CO may be less than 10ppm or less than 50% Baseline CO). This stringent biochemical criterion for validating smoking cessation has been shown to be more sensitive to detect smoking and specific to verify abstinence than higher CO cut-offs [69].

Carbon Monoxide. Carbon monoxide (CO) measures will be made using a Vitalograph Breath CO Analyzer (McNeil International, Inc., Lenexa, KS). The manufacturer will have calibrated this device within the past year. A new, disposable cardboard mouthpiece will be provided for each participant. The device has a digital screen which reports CO levels in parts per million (ppm). Participants will be asked to provide a CO breath sample by taking a large breath then exhaling twice. Then, they will take another deep breath and hold their breath for 10 seconds, as per the recommendations of the American Thoracic Society. Then, when instructed to do so, participants will exhale as forcefully and as long as they are comfortably capable. The largest value displayed is recorded during all CO breath samples. CO breath samples will be collected at each study visit. At the Intake, participants must have CO readings greater than or equal to 10ppm in order to be eligible for the study.

2. Statistical Analysis

Sample size.

Effect sizes for power analyses were derived from prior work on TN effects on days of abstinence (Aim 1) [6], studies demonstrating RAM's effects on sleep (Aim 2), and our preliminary data. All significance levels will be set at 0.05. Our primary hypothesis is that RAM will increase the number of days abstinent (out of 5), compared to placebo. In prior validation work, the average number of days abstinent for TN was 2.0 ± 0.3 [6]. Fifty subjects provide 80% power to detect a difference of 0.55 days between RAM and PLA, using a SD of 1.36 and a within-subjects correlation of 0.78 [31].

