For Aim 2, meta-analyses indicate that RAM is associated with reducing SOL by 4.3 min and increasing sleep efficiency by 4.42% [70]. Our preliminary data suggest that TN increases sleep disturbance by 58% ($d=0.28$) in abstinent smokers and that abstinence increases SOL by ~5 min and decreases sleep efficiency by ~5%. Fifty subjects provide 80% power to detect differences of 6 min in SOL and 5% in sleep efficiency between RAM and PLA, using a within-subject correlation between 0.4 and 0.8. Thus, Aims 1 and 2 are sufficiently powered.

Statistical Analysis.

For Aim 1 (H1), a within-subject ANOVA will test the primary hypothesis for effects of RAM (vs. PLA) on number of days abstinent during the quit week.

For Aim 2 (H2a), separate 2 drug (RAM vs. PLA) x 2 week (baseline vs. quit week) repeated measures ANOVAs will test the effects of RAM on SOL and sleep efficiency. Drug and week are within-subject factors and sleep measures will be averaged across days within each baseline and quit week. We are primarily interested in the drug x week interaction to test whether RAM (vs. placebo) attenuates sleep disturbance during the quit week, relative to baseline. Thus, each period has its own baseline control comparison. A supplemental analysis will include only days during the quit week when subjects are abstinent.

For Aim H2b, linear regression models will test whether sleep disturbance predicts number of days abstinent and

whether this relationship varies by treatment. Models will include covariates (e.g., baseline depression/anxiety, FTND, sex, and age). We will also examine correlations between sleep disturbance data and nicotine withdrawal and depression/anxiety symptoms in both groups.

3. Confidentiality

All participant information will be kept in a secure filing cabinet that is accessible only to authorized study personnel. All study databases containing participant information will be password protected, and accessible only to authorized study personnel. Any study communications made by e-mail will use ID numbers and not include names or other personal information. All data sets will use ID numbers only.

How will confidentiality of data be maintained? Check all that apply.

- Paper-based records will be kept in a secure location and only be accessible to personnel involved in the study.
- Computer-based files will only be made available to personnel involved in the study through the use of access privileges and passwords.

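### The withdrawal score includes an insomnia item, so the exploratory sleep–withdrawal correlation has sleep content on both sides and leans toward an association

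*Combined protocol and SAP*

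**What the plan says.** Section 3.3 (Withdrawal Symptoms) lists the eight items of the MNWS-R: "dysphoria or depressed mood, insomnia, irritability/frustration/anger, anxiety, decreased heart rate, difficulty concentrating, restlessness, and increased appetite/weight gain". Each is rated 0 to 4, "and a summary score will be calculated. This will be administered at all study visits (except the Intake"). On timing, "Withdrawal will be assessed using a 24-h time reference for all visits following the Intake".

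Sleep is measured in two ways. For the diaries, section 3.3 says: "These well-validated sleep diaries assess subjective SOL, total sleep time, number of awakenings and perceived quality of sleep". The Protocol Abstract names the two sleep outcomes: "Intermediate outcomes include sleep onset latency (self-report) and sleep efficiency (SensewearPro® armband").

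The Statistical Analysis section, at the end of the Aim H2b paragraph, brings the two together: "We will also examine correlations between sleep disturbance data and nicotine withdrawal and depression/anxiety symptoms in both groups". No section says that the insomnia item is left out, that a score without it is formed, or that the correlation is run item by item.

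**The concern.** A participant who sleeps badly can record it in the diary and again in the insomnia rating of the withdrawal scale. If the insomnia rating is part of the withdrawal total, some of the correlation between sleep and withdrawal is sleep correlated with itself. A non-zero result then cannot be read cleanly as a link between sleep and the rest of the withdrawal syndrome, which is the only reading that would be informative.

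The overlap should be strongest against the diary measures, because both sides are then self-reports and the withdrawal scale looks back only 24 hours. It is probably weaker against armband sleep efficiency, which a device measures. What is at stake is the interpretation of one exploratory analysis in a pilot meant to inform a larger trial.

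**Working it through.** The plan states no figure for this correlation, so there is nothing to reproduce. The overlap can be sized by part-whole algebra.

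**Inputs from the documents**
- Items in the scale: 8, of which insomnia is one (section 3.3).
- Rating 0 to 4 per item. If the summary score is a simple sum, its maximum is 8 × 4 = 32, and the insomnia item can supply 4/32 = 12.5% of it.
- Completers: 50 (section 4.1).
- Test level: "All significance levels will be set at 0.05". Sidedness is not stated; two-sided is assumed.

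**Inputs assumed, because the documents do not give them**
- Equal item variances.
- Inter-item correlation r = 0.2 to 0.5.
- Correlation of the insomnia item with the sleep measure q = 0.3 to 0.7.
- Correlation of each other item with the sleep measure s = 0 to 0.2.
- The sleep measure is coded so that higher means worse sleep.

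**Formulas**
- Eight-item score with sleep: (7s + q) / √(8 + 56r)
- Seven-item score with sleep: 7s / √(7 + 42r)

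**Case 1: the other seven items are unrelated to sleep (s = 0).** The seven-item correlation is exactly 0. The eight-item correlation is q / √(8 + 56r):

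| r | q = 0.3 | q = 0.5 | q = 0.7 |
|---|---|---|---|
| 0.2 | 0.068 | 0.114 | 0.160 |
| 0.3 | 0.060 | 0.100 | 0.141 |
| 0.4 | 0.054 | 0.091 | 0.127 |
| 0.5 | 0.050 | 0.083 | 0.117 |

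For example, 0.7 / √(8 + 11.2) = 0.7 / 4.382 = 0.160, and 0.3 / √(8 + 28) = 0.3 / 6 = 0.050.

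**Case 2: the other items do relate to sleep, with q = 0.5.** Ranges run from r = 0.5 to r = 0.2.
- s = 0.1: seven items 0.13 to 0.18; eight items 0.20 to 0.27.
- s = 0.2: seven items 0.26 to 0.36; eight items 0.32 to 0.43.

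At each r, the upward shift is 0.08 to 0.11 when s = 0, 0.07 to 0.10 when s = 0.1, and 0.05 to 0.08 when s = 0.2. It shrinks as the true link grows but does not vanish.

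**When it reverses.** The two scores give the same correlation when q = 7s × (√[(8 + 56r)/(7 + 42r)] − 1). That is q of about 0.08 to 0.09 for s = 0.1, and 0.16 to 0.19 for s = 0.2. The shift is downward only if the insomnia item tracks the sleep measure slightly less well than the other symptoms do.

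**Effect on a test at n = 50.** With one pair of values per completer, the critical |r| is 2.011 / √(48 + 2.011²) = 0.279. By the Fisher z approximation (standard error 1/√47), an overlap-only correlation of 0.10 reaches p < 0.05 in about 11% of trials, and one of 0.16 in about 20%, instead of 5%.

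**The case against.** The strongest reply is that the analysis is peripheral. It is a single sentence with no hypothesis number and no power statement, and it is not among the outcomes listed under Objectives. Insomnia is also presented as a DSM-IV withdrawal symptom, so the full score is the named scale used as intended. All of this stands and limits the weight of the point. It does not remove the overlap.

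The size is also wholly conditional on assumed correlations. The plan does not say whether nights and ratings are paired by day or averaged over the week, so same-night matching is itself an assumption. That stands too.

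A reader might infer more than the documents support:
- *That the correlation is positive by construction.* It is biased toward an association, not fixed. Armband sleep efficiency is device-measured and runs the other way (higher is better), so the expected sign there is negative and q may be low.
- *That the overlap could produce a correlation near 0.25.* This needs 0.7 / √8 = 0.247, that is, zero correlation among symptoms combined into one score. That is implausible.
- *That ramelteon would appear to relieve withdrawal through its effect on sleep.* The Statistical Analysis section plans no drug comparison on the withdrawal score, so this arises only if one is later reported.
- *That the trial's rationale is undermined.* The tests that carry it do not use the score. If the question were whether sleep is separate from the rest of withdrawal, an inflated correlation would count against the hypothesis rather than flatter it.
- *That the anxiety variable has the same defect.* No dedicated anxiety scale is named, but the Potential Study Risks section says anxiety is also queried on the side effects checklist. This is a separate matter of missing detail and forms no part of this point.

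**Conclusion.** The point holds, at modest size. As written, the sleep–withdrawal correlation uses a score that contains a sleep item, and this biases it toward an association, chiefly for the diary measures. Under the stated assumptions (equal item variances, r = 0.2 to 0.5, q = 0.3 to 0.7, s = 0), the overlap alone contributes about 0.05 to 0.16. That is below the 0.279 needed for significance at n = 50, but enough to raise the false-positive rate at the upper values. The documents do not allow a firmer figure.

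H1 (days abstinent), the H2a ANOVAs on sleep onset latency and sleep efficiency, the H2b regression of days abstinent on sleep disturbance, and the sample size do not draw on this score as described, so none is affected. I would class this as a free improvement, not a defect in the trial's main conclusions.

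**What to change.** Add a sentence to the Aim H2b paragraph of the Statistical Analysis section: correlations between sleep measures and nicotine withdrawal use the MNWS-R score computed without the insomnia item (seven items, maximum 7 × 4 = 28 if summed), and the full eight-item score is shown alongside for comparability. Apply the same rule if a ramelteon effect on withdrawal is ever reported.

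The cost is wording only. Participants already rate each symptom, so no new data, visits or participants are needed. The one downside is that a seven-item score departs from the named scale, and reporting both scores deals with that.

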3.4 Smoking Outcomes

Smoking Rate (TLFB). We will assess the number of cigarettes smoked on each day throughout the study. A standard timeline follow-back (TLFB) method will be used [67], as we have done previously [68] to assess self-reported smoking rate. During each quit week, abstinence will be assessed daily by self-report of no smoking at all over the prior 24 hours and an expired-air CO less than 5 ppm (except for the Monday visit when CO may be less than 10ppm or less than 50% Baseline CO). This stringent biochemical criterion for validating smoking cessation has been shown to be more sensitive to detect smoking and specific to verify abstinence than higher CO cut-offs [69].

Carbon Monoxide. Carbon monoxide (CO) measures will be made using a Vitalograph Breath CO Analyzer (McNeil International, Inc., Lenexa, KS). The manufacturer will have calibrated this device within the past year. A new, disposable cardboard mouthpiece will be provided for each participant. The device has a digital screen which reports CO levels in parts per million (ppm). Participants will be asked to provide a CO breath sample by taking a large breath then exhaling twice. Then, they will take another deep breath and hold their breath for 10 seconds, as per the recommendations of the American Thoracic Society. Then, when instructed to do so, participants will exhale as forcefully and as long as they are comfortably capable. The largest value displayed is recorded during all CO breath samples. CO breath samples will be collected at each study visit. At the Intake, participants must have CO readings greater than or equal to 10ppm in order to be eligible for the study.

2. Statistical Analysis

Sample size.

Effect sizes for power analyses were derived from prior work on TN effects on days of abstinence (Aim 1) [6], studies demonstrating RAM's effects on sleep (Aim 2), and our preliminary data. All significance levels will be set at 0.05. Our primary hypothesis is that RAM will increase the number of days abstinent (out of 5), compared to placebo. In prior validation work, the average number of days abstinent for TN was 2.0 ± 0.3 [6]. Fifty subjects provide 80% power to detect a difference of 0.55 days between RAM and PLA, using a SD of 1.36 and a within-subjects correlation of 0.78 [31].

For Aim 2, meta-analyses indicate that RAM is associated with reducing SOL by 4.3 min and increasing sleep efficiency by 4.42% [70]. Our preliminary data suggest that TN increases sleep disturbance by 58% ($d=0.28$) in abstinent smokers and that abstinence increases SOL by ~5 min and decreases sleep efficiency by ~5%. Fifty subjects provide 80% power to detect differences of 6 min in SOL and 5% in sleep efficiency between RAM and PLA, using a within-subject correlation between 0.4 and 0.8. Thus, Aims 1 and 2 are sufficiently powered.

Statistical Analysis.

For Aim 1 (H1), a within-subject ANOVA will test the primary hypothesis for effects of RAM (vs. PLA) on number of days abstinent during the quit week.

For Aim 2 (H2a), separate 2 drug (RAM vs. PLA) x 2 week (baseline vs. quit week) repeated measures ANOVAs will test the effects of RAM on SOL and sleep efficiency. Drug and week are within-subject factors and sleep measures will be averaged across days within each baseline and quit week. We are primarily interested in the drug x week interaction to test whether RAM (vs. placebo) attenuates sleep disturbance during the quit week, relative to baseline. Thus, each period has its own baseline control comparison. A supplemental analysis will include only days during the quit week when subjects are abstinent.

For Aim H2b, linear regression models will test whether sleep disturbance predicts number of days abstinent and

whether this relationship varies by treatment. Models will include covariates (e.g., baseline depression/anxiety, FTND, sex, and age). We will also examine correlations between sleep disturbance data and nicotine withdrawal and depression/anxiety symptoms in both groups.

3. Confidentiality

All participant information will be kept in a secure filing cabinet that is accessible only to authorized study personnel. All study databases containing participant information will be password protected, and accessible only to authorized study personnel. Any study communications made by e-mail will use ID numbers and not include names or other personal information. All data sets will use ID numbers only.

How will confidentiality of data be maintained? Check all that apply.

- Paper-based records will be kept in a secure location and only be accessible to personnel involved in the study.
- Computer-based files will only be made available to personnel involved in the study through the use of access privileges and passwords.
- Prior to access to any study-related information, CIRNA personnel will be required to sign statements agreeing to protect the security and confidentiality of identifiable information.
- Whenever feasible, identifiers will be removed from study-related information.
- A Certificate of Confidentiality will be obtained, because the research could place the subject at risk of criminal or civil liability or cause damage to the subject's financial standing, employability, or liability.
- A waiver of documentation of consent is being requested, because the only link between the subject and the study would be the consent document and the primary risk is a breach of confidentiality. (This is not an option for FDA-regulated research.)
- Precautions are in place to ensure the data is secure by using passwords and encryption, because the research involves web-based surveys.
- Audio and/or video recordings will be transcribed and then destroyed to eliminate audible identification of subjects.
- Other (*specify*): ____

All research personnel associated with this study have completed the CITI-Protection of Human Subjects Research Training as well as HIPAA Compliance Training. Trained staff will assess eligibility, introduce the study rationale, procedures, study risks, and collect combined informed consent/ HIPAA authorization form.

5. Privacy

The following protected health information will be collected as part of this study:

- Name
- Street address, city, county, zip code
- Telephone numbers
- Email address
- Date of birth
- Medical and drug use history
- Last 4 digits of Social Security Number
- Results from all questionnaires, tests, or procedures
- Data collected from SensewearPro armbands
- Urine for drug screening/pregnancy test
- Blood for liver function test (for those with history of jaundice/liver disease)

6. Tissue Specimens

Urine. A urine sample will be required at all sessions for the drug and pregnancy screening. Participants who test positive for study prohibited drugs use will be deemed ineligible, as will women who have a positive pregnancy test. All female participants of child-bearing potential will complete urine pregnancy tests.

Blood. (only for those with history of jaundice/liver disease) An 8.5ml sample of blood will be drawn at the Intake visit to evaluate liver function.

RISK/BENEFIT ASSESSMENT

1. Potential Study Risks

Potential Risks of the Medication: The following are the common side effects that have been reported with ramelteon treatment: drowsiness, tiredness, dizziness, and nausea. All of these side effects have been mild and

transient in nature. These symptoms have occurred in approximately 3% of subjects in clinical trials (Takeda Pharmaceutical, 2005). Side effects will be assessed at baseline of each period and each subsequent visit (a total of 16 times throughout the study). The incidence of side effects is lower with the 8mg dose (as compared to the 16mg dose); which is the dose that has been selected in the proposed project.

In addition to the side effects mentioned above, other rare side effects of ramelteon have been reported:

- Severe anaphylactic and anaphylactoid reactions such as angioedema (swelling of the tongue and larynx), difficulty swallowing, vomiting, and throat closing.
- Abnormal thoughts and behavioral changes such as hallucinations, suicidal thoughts, bizarre behavior, agitation and mania, amnesia, and anxiety
- Complex behaviors such as "sleep-driving" and other behaviors (e.g., preparing and eating food, making phone calls)
- Hormone effects including decreased testosterone and increased prolactin

All of these side effects shall be queried using a side effects checklist as described above.

Stringent exclusion criteria are in place to limit the chance of these side effects. Additionally, participants will be informed about these possible side effects and be made aware to watch for any of these symptoms and report them as soon as possible to the research staff. All subjects will be instructed to take the study medication 30 minutes before going to bed. They will also be warned they should not drive or operate machinery after taking ramelteon and that they should limit their consumption of alcohol. All side effects will be closely monitored and the study physician consulted should moderate or severe side effects be reported. In case any participant experiences severe side effects or an adverse event, they will be encouraged to contact the study physician ([name]) and study PI ([name]) immediately for appropriate intervention. The study physician's emergency contact numbers shall be on the medication blister pack, the study consent form, and a study brochure all participants will be provided with once they enroll into the study.

Transdermal Nicotine (TN) Replacement Therapy: All participants will receive transdermal nicotine (TN) patch therapy to aid in quitting smoking. This therapy is available over the counter and is very well tolerated. Participants will use the 21 mg patch for 5 days during each quit assessment week. Nausea, vomiting, weakness, dizziness, and rapid heartbeat occur rarely and are most often caused by continuing to smoke while using the patch. In addition, there is a risk of peptic ulcer formation and delayed wound healing associated with nicotine replacement therapies. Some individuals who use the patch experience minor skin irritation, such as redness, rash, or minor swelling, and insomnia and dream abnormalities. Because sleep problems are a primary mechanism of interest, participants will be instructed to remove the patch during the night while sleeping to avoid dream abnormalities. All of these reactions cease once the patch is removed.

During the third visit of each baseline week (weeks 1 and 5), a member of the research staff will review the purpose of using the nicotine patch (e.g., to help manage withdrawal symptoms; not a substitute for behavioral quitting strategies), provide directions on how to use the patch (e.g., abstinence from smoking, patch location, time, activity, and potential skin reactions), and answer any questions.

Because increased blood pressure is a side effect of TN patch therapy, blood pressure will be closely monitored at each visit. Expanding the upper limit of the blood pressure to less than 160/100 does not increase the risk to subjects enrolled in this trial. The risk of increased blood pressure is no greater than the risk from smoking and quitting smoking will lower an individual's risk. If a participant presents with a SBP between 151-159 mmHg and/or DBP between 91-99 mmHg at the Intake or Pre-Quit visit, the research staff will inform the participant that they have mild, Stage I, hypertension and advise they consult with a physician. The participant will remain eligible for the study and receive nicotine patches as scheduled.

Participants will complete a patch side effects checklist at each visit (in addition to those listed above for ramelteon). The PI will review the checklists for serious and persistent side effects. These will be communicated immediately to the study physician, [name]. Participants will be instructed to promptly discontinue the patch and contact the PI if they experience severe or persistent local skin reactions (e.g., severe redness, itching, or swelling) at the site of patch application or a generalized skin reaction (e.g., raised patches, hives, or generalized rash). Any serious adverse reactions or significant side effects of TN will be medically evaluated by the study physician. Patch use by such individuals will be monitored and adjusted as needed. Based on our previous

experience with NRT studies [30, 31], we expect few serious adverse events. Nevertheless, the study physician, [name], will be available to assist with any adverse events and participant safety issues. Depending on the nature of the side effects, [name] may reduce the dose of the patch or recommend that the participant discontinue the patch.

Pregnancy: In animal studies, ranelteon produced evidence of developmental toxicity, including teratogenic effects, in rats at doses much greater than the recommended human dose (RHD) of 8 mg/day. There are no adequate and well-controlled studies in pregnant women. Thus, ranelteon must not be used during pregnancy. All female participants of child bearing potential must have a negative pregnancy test at the Intake session and prior to receiving study medication (Baseline Visit 3 of each medication period).

Blood Draw: (only for individuals with a history of liver disease/jaundice) Blood draws may result in bruising and/or slight bleeding at the needle site. This is rare and happens infrequently. Occasionally, blood drawing results in a feeling of faintness. This too is rare. A trained professional will draw blood, so the chances of these discomforts are minimal.

Confidentiality and Loss of Privacy: Protection of privacy of subjects in research studies is of utmost importance, particularly when health history information is collected. Information will never be recorded with identifiers other than study ID. A separate list of names with ID numbers will be accessible only by the database manager. All records will be kept in locked filing cabinets to maintain confidentiality. Results will not be communicated to other personnel or to the subjects. All analyses will be conducted on de-identified data.

Withdrawal: Many individuals who smoke cigarettes exhibit a pattern of symptoms associated with withdrawal from cigarette use. These symptoms can include: sadness and anxiety, irritability, difficulty concentrating, anger, appetite change and weight gain, insomnia, and decreased heart rate. These events are generally of low risk. The study personnel will be trained to recognize these symptoms and educate the participants about them (e.g., their duration, methods for reducing them). TN will also help reduce withdrawal symptoms.

Assessments: Subjects may experience emotional distress during assessments, from discussing feelings and attitudes about smoking, or from learning about the risks from smoking. These events happen very rarely and in almost all cases are short-lived and of low intensity. Study personnel will be alerted to expect this from a small number of subjects and will be trained to make referrals for mental health services as needed. Personnel will be trained to query for adverse emotional reactions during assessments and will be trained to deal with such reactions and to provide additional referrals if needed. In addition, if assessments indicate psychiatric concerns, referrals to appropriate psychological services will be provided.

2. Potential Study Benefits

Participants who enroll in this study will benefit from the knowledge that they are contributing in an important way to potentially furthering scientific knowledge concerning ways to improve smoking cessation treatment. All smokers will receive standard treatment with TN to aid them in their effort to quit smoking and will learn skills to stay quit as a result of participating.

3. Alternatives to Participation

At any point in the study participants may decide not to continue in their participation. As an alternative to enrolling in this study, participants may choose to continue to smoke or to seek assistance with quitting smoking through other treatment programs located in the area, other quit-smoking studies at our Center, or contacting the national quit-line.

4. Data and Safety Monitoring

Who will monitor this study? Check all that apply.

- Principal Investigator
- Sponsor or contract research organization
- NCI sponsored cooperative group
- Cancer Center (if mandated by CTSMRC)
- Medical monitor
- Safety monitoring committee

Data and safety monitoring board

